3. RESEARCH METHODOLOGY

Hypothesis:

The morning chronotype and early meal-timing are associated with low glycemic outcome among prediabetic individuals.

Research Questions:

Is the morning chronotype and early meal-timing are associated with better glucose tolerance among prediabetic individuals?

General objective:

To determine the associations of chronotype and chrononutrition with glucose tolerance among prediabetic individuals in Malaysia.

Specific objectives:

1. To examine the associations among chronotype, chrononutrition and glucose outcomes.
2. To investigate the association between lifestyle factors (physical activity level, light exposure, diet timing, sleep pattern) and chrononutrition.
3. To investigate the association between anthropometry measurements and glycemic outcomes.

Description of Methodology:

Participants will be recruited using the convenience sampling method. The proposed study will be conducted in community clinics in Malacca, Malaysia. Malacca is the capital of the coastal state, located in southwestern Malaysia, with an estimated total population of 0.93 million in the year 2019 (Department of Survey and Mapping Malaysia, 2021). In 2019, National Health and Morbidity Survey reported that 17% of Malaccan adults had hyperglycemia and 13.7% of them had known diabetes. Malacca is 1 out of the top five states showing the highest prevalence of diabetes in Malaysia (IPH, NIH and MOH, 2019). Permission to carry out data collection has been granted by the Medical Research and Ethics Committee (MREC) (RSCH ID-21-00114-IVI). The study protocol has been reviewed and approved by the Tunku Abdul Rahman University College (TARUC) research ethics committee (TAR UC/EC/2021/02-3).

During the process of recruitment, a trained research assistant (one of the co-researcher), clinical dietitian (one of the co-researcher) or family medicine specialist

(one of the co-researcher) will inform potential prediabetic individuals research protocol verbally and written information will be provided. Newly diagnosed prediabetic individuals who are agreeable to participate will provide written informed consent. Baseline and follow up appointments will be determined based on the community clinic appointment schedules. Those who decline to participate will continue to receive their routine treatment as usual, and care provided to each prediabetic individual will not be affected by the decision to either participate or not participate in the study.

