The sample size is estimated using G*Power software version 3.1.9.4 (Erdfelder, Faul and Buchner, 1996). To determination of association between chrononutrition and glycemic control, the β -coefficient of 0.13 adopted from Sakai *et al.*, (2018), the power was set to 0.9 with 2 sided significance level and alpha error given 0.05, a total of 83 prediabetic adults expected in this study. To compensate for the non-responding and non-compliance during follow-up, a dropout rate of 50% will be considered, the total sample size required is 166 subjects in the study for 6 months.

Test Family: T Test

Statistical Test: Linear Multiple Regression Fixed Model, single regression coefficient

Tail(s): 2

Effect Size (β -coefficient): 0.13 (Sakai *et al.*, 2018)

α Error prob: 0.05

Power(1- β err prob): 0.90

[figure not shown]
Total Sample Size: 83 prediabetes individuals

50% dropout rate taken as consideration in study for 6 months follow up, total 166 prediabetes individuals shall be recruit in this study.

Dropout Rate:

$$= \frac{83}{1-0.5} = 166 \text{ prediabetic individuals}$$

Figure 3: Flow diagram of the study design

Participants will be undergoing OGTT, FBS and HbA1c tests after an overnight fast of 8-10 hours. This is a routine universal test for prediabetes/ diabetes diagnosis. Participants will be informed to eat their usual diet for three days prior to the test. The diagnostic value for diabetes on plasma glucose. the diagnostic values for prediabetes and diabetes based on OGTT, and the diagnostic values for prediabetes and diabetes based on HbA1c have been shown in Table 1, Table 2 and Table 3, respectively. Fasting blood sample will be taken for FBS and HbA1c tests. Subsequently, participants will be given 75-gram glucose water to drink within 5 minutes. Blood sample will be taken after 2 hours for glucose determination. Participants should rest throughout test with only plain water is allowed to drink. Figure 4 shows the procedure of OGTT. All the tests will be conducted in the healthcare clinic lab. Results will be traced from medical record.

Table 4: Summary of data collection and timeline

Data	Baseline	3 months	6 months
Sociodemographic			
Age	.	.	.
Date of Birth	.	.	.
Marital Status	.	.	.
Education Level	.	.	.
Occupation	.	.	.
Monthly Household Income	.	.	.
Health History	.	.	.
Smoking Habit	.	.	.
Supplementary Consumption	.	.	.
Anthropometry			
Weight	.	.	.
Height	.	.	.
Waist Circumference	.	.	.
Visceral Fat	.	.	.
Body Fat	.	.	.

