pattern from the validated questionnaires PSIQ and light exposure from the validated questionnaire HLEQ.

Statistical Analysis

All data will be performed statistical analysis using the SPSS software version 20 (SPSS Inc., Chicago, IL, USA). The socio-demographic will be presented as mean, standard deviations, median, interquartile range, frequency, and percentage. Data cleaning will be performed to exclude the outlier data before the normality is checked using Kolmogorov-Smirnov Test. The investigator considered $p < 0.05$ to be statistically significant. Chronotype, sleep quality, and light exposure will be analyzed as categorical variables whereas dietary intake, chrononutrition, anthropometry, glycemic measure, and physical activity will be analyzed as continuous variables.

The investigator will perform a multivariable generalized linear model to examine the association between night meal pattern (last night mealtime either dinner or supper with calories intake, frequency of night snacking, and the total number of the night snacking) and glycemic outcome (HbA1c, FPG, 2hPPG, CGM profile) by adjusting for the potential covariates. Specifically, nighttime will be characterized by the time range from 1900 and 0659 hours based on Malaysia solar time. The investigator will explore the late-night meal timing in 2000, 2100, and 2200 to examine its association with glycemic outcomes. The potential confounders include sociodemographic characteristics, physical activity, sleep pattern, sedentary behavior, diet quality, and light exposure will be controlled. ANCOVA test will be performed to understand the association between chrononutrition (breakfast skipping, meal frequency, eating window, sleep timing, chronotype, and fasting pattern) with glycemic variables, controlling for potential covariates (sociodemographic characteristics, light exposure, diet quality, physical activity and sleep pattern).

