APPENDIX D
Munich Chronotype Questionnaire

8

9

Meal Timing and Glucose Tolerance

10

Project Name:

		/				/					11
d	d		m	m	m		y	y	y	13	12

13

14

15

16

Munich Chronotype Questionnaire (MCTQ)

17

18

This questionnaire requires you to report your sleep patterns over the past 4 weeks. Working day and non -working day sleep patterns were asked separately. Please answer this question according to your perceptions of your weekly habits, workday sleep patterns and non -working days.

[figure not shown]
23

I have regular working hours (this includes housewives):

24

 Yes, I work	 1	 2	 3	 4	 5	 6	 7		Day/week
 No									

If your answer is 'Yes, 7 days' or 'No', please consider whether your bedtime may differ between normal weekdays and weekends and fill out the MCTQ accordingly.

26

27

Based on the following picture, answer the question below (Please answer on a 24 -hour scale, for example; 23:00):

30

Working Days		
Picture 1	I entered the bedroom at: _____	
Picture 2	Some people stay awake even after lying in bed.	
Picture 3	I'm ready to go to bed at (turn off the lights and go to sleep): _____	
Picture 4	How many minutes do I need to sleep: _____	
Picture 5	I woke up in the morning at: _____	
Picture 6	I got out of bed after a few minutes: _____	
I use an alarm clock on weekdays		Yes  No
If YES, I usually wake up BEFORE the alarm clock rings:		Yes  No
Weekend		
Picture 1	I entered the bedroom at: _____	
Picture 2	Some people stay awake even after lying in bed.	

Picture 3	I'm ready to go to bed at (turn off the lights and go to sleep): _____			
Picture 4	How many minutes do I need to sleep: _____			
Picture 5	I woke up in the morning at: _____			
Picture 6	I got out of bed after a few minutes: _____			
My waking hours were due to the use of an alarm clock (Figure 5):		Yes		No

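### Chronotype, one of the two exposures in the hypothesis, is to be analysed in unspecified categories although its questionnaire yields a continuous sleep time

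*Combined protocol and SAP*

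**What the plan says.** The hypothesis in section 3 (Research Methodology) names two exposures: "The morning chronotype and early meal-timing are associated with low glycemic outcome among prediabetic individuals". Chronotype is also in the study title, the general objective and the first specific objective of that section, and its change at 6 months is a secondary outcome in the synopsis.

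The Statistical Analysis part of section 3 sets the variable types. Chronotype is on the categorical list: "Chronotype, sleep quality, and light exposure will be analyzed as categorical variables". The exposure that was powered is on the other list, which reads "whereas dietary intake, chrononutrition, anthropometry, glycemic measure, and physical activity will be analyzed as continuous variables". The section states no number of chronotype groups and no cut-points. Further on, the ANCOVA sentence counts both chronotype and sleep timing among the components of chrononutrition.

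The MCTQ form in Appendix D asks, separately for working days and weekends, when the respondent is ready to sleep, how many minutes falling asleep takes, and when they wake. Its instruction on format is "Please answer on a 24 -hour scale, for example; 23:00".

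The only power calculation opens "To determination of association between chrononutrition and glycemic control". It uses a "coefficient of 0.13 adopted from" a published cohort study of late dinner in type 2 diabetes, and "the power was set to 0.9 with 2 sided significance level and alpha error given 0.05". The procedure is "Statistical Test: Linear Multiple Regression Fixed Model, single regression coefficient", which gives 83 evaluable participants, or 166 recruited.

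**The concern.** Three things are at stake.

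- **Information.** The form collects times to the minute. Grouping treats everyone within a group as identical. For the secondary outcome, a change in sleep timing would register only if a participant crossed a boundary that the plan does not define.
- **Fit to the question.** The rationale in the literature review (Chrono-type and blood glucose homeostasis) is graded: it speaks of later and earlier types and of phase shifts of 2-3 hours between extremes. An unordered group comparison in ANCOVA does not test a gradient directly.
- **Dependence on later choices.** With groups and cut-points left open, and four glycemic measures to relate them to, the chronotype result could differ according to a choice made after the data are available.

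Separately, the section contradicts itself. Chronotype is categorical in one sentence and part of a set declared continuous when that sentence is read with the ANCOVA sentence.

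**Working it through.** **Step 1: reproduce the plan's figure.** Inputs from Sample size Calculation: f² = 0.13 (the value entered as effect size), two-sided α = 0.05, power 0.90, one coefficient. Noncentral t with δ = √(f²·N) and N − p − 1 degrees of freedom. At N = 83, δ = √(0.13 × 83) = √10.79 = 3.28, and power is 0.901 with one predictor. The plan's 83 is reproduced, and 83/(1 − 0.5) = 166 follows.

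**Step 2: state the assumptions for chronotype.** The plan gives no chronotype effect size, group number or group shares. For illustration, assume that f² = 0.13 applies to continuous chronotype, that chronotype is normal and linearly related to the outcome, and that 83 are evaluable. Then R² = 0.13/1.13 = 0.115.

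**Step 3: share of exposure variance kept by grouping.** For two groups with proportions q and 1 − q cut at c, the share is φ(c)²/[q(1 − q)]. For k groups it is the between-group variance of the group means of a standard normal. The reduced R² is 0.115 × share, and f² = R²/(1 − R²). Power is then recomputed with noncentral t (two groups) or noncentral F with k − 1 numerator degrees of freedom (three groups).

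Worked example, median split: the share is 2/π = 0.637, R² = 0.115 × 0.637 = 0.0732, f² = 0.0732/0.9268 = 0.0790, and δ = √(0.0790 × 83) = 2.56. Power is 0.716.

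| Chronotype in the model (N = 83) | Share kept | Power |
|---|---|---|
| Continuous | 1.000 | 0.90 |
| Two groups, 50/50 | 0.637 | 0.72 |
| Two groups, 33/67 | 0.593 | 0.68 |
| Two groups, 25/75 | 0.539 | 0.64 |
| Two groups, 20/80 | 0.490 | 0.60 (0.595) |
| Three groups, tertiles | 0.793 | 0.72 |
| Three groups, 25/50/25 | 0.808 | 0.73 |
| Three groups, 20/60/20 | 0.784 | 0.71 |
| Three groups, 10/80/10 | 0.616 | 0.59 |

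Under the same assumptions, returning to 0.90 would need 135 evaluable participants with a median split, or 130 with tertiles, against 83.

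**Step 4: sensitivity.**

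- Tertiles scored as a one-degree-of-freedom trend give 0.81, so part of the loss comes from ignoring the order of the groups.
- With 120 evaluable (the synopsis sample size, no dropout), 0.975 falls to 0.80-0.86 for two-group splits between 25/75 and 50/50. With 60 evaluable (120 less 50%), 0.78 falls to 0.50-0.57.
- If 0.13 is a standardised coefficient rather than f², then f² = 0.0169/0.9831 = 0.017. Power at N = 83 is then 0.22 continuous and 0.16 after a median split. That is a separate question about the 0.90 baseline, but grouping still loses power.

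**The case against.** The strongest case against has five parts.

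1. **No stated power is reduced.** A reader might infer that grouping takes the plan's 90% power down to 64-72%. The documents do not support that. The 0.90 is for chrononutrition, which stays continuous, and no effect size or power is claimed for chronotype. The ANCOVA sentence does place chronotype inside chrononutrition, but that shows an inconsistency, not a power claim. This objection stands, and the figures above are conditional.

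2. **The 0.13 may already describe a grouped exposure.** The literature review describes the source study's exposure as dinner after 8 pm, which reads as yes/no, and a two-group indicator is itself a single coefficient. If f² = 0.13 were the effect of the grouped variable, power at N = 83 would be 0.90 for two groups and 0.83 for three. This limits the size of the claim. It does not change the fact that cutting a continuous exposure loses information when the relation is close to linear.

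3. **The hypothesis names a type.** A morning-versus-other contrast matches its wording. That is fair, but such a contrast still needs a definition of morning type, and none is given.

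4. **Sleep timing is listed separately in the ANCOVA, and sleep duration is modelled elsewhere.** Some continuous sleep information may therefore be analysed. Sleep timing is not defined or tied to the MCTQ, however, so it does not settle how chronotype is tested.

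5. **Continuous mid-sleep needs rules.** Appendix D records weekend alarm use, constraints on bedtime and return to sleep, and it allows for respondents who work seven days or have no regular hours. This stands and is taken into the fix.

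**Conclusion.** The concern holds in conditional form. Chronotype is to be grouped with no stated number of groups or cut-points although its instrument gives clock times, and the same section is inconsistent about whether it is categorical or continuous. Both points rest on the text alone.

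The size of the loss rests on assumptions that the plan does not state: f² = 0.13 for chronotype, a normal exposure, a near-linear relation and 83 evaluable. On those, power falls from 0.90 to about 0.64-0.72 for common splits, and lies at about 0.59-0.73 across the two- and three-group unordered splits examined.

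The protocol is dated 6 May 2024 and its research schedule ends third visits on 06/03/2024, so a reader might infer that cut-points were chosen with data in hand. The documents do not show this; they only leave it open. Nor does the point extend to sleep quality, which is not in the hypothesis and for which no loss has been shown.

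This is a worthwhile, inexpensive improvement and not a flaw that invalidates the study.

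**What to change.** In the Statistical Analysis section:

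- Make continuous mid-sleep time from the MCTQ the main chronotype exposure in the adjusted model. Sleep onset is the ready-to-sleep time plus the minutes to fall asleep, and mid-sleep is halfway from onset to waking.
- Add a quadratic or spline term as a check for curvature.
- State how mid-sleep is derived when an alarm is used on free days, when the respondent goes back to sleep, and when there are no distinct free days.
- Keep morning, intermediate and evening groups for descriptive or secondary use, with number and cut-points fixed in advance of the analysis.
- Reconcile the two statements on variable type, saying whether chronotype is part of chrononutrition and on what scale it is analysed.

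Cost: a short paragraph and a few derivation rules, using data that the form already collects. The downside is reliance on a near-linear relation, which the curvature term checks.

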Management of excessive caloric intake and promote on exercise are both core lifestyle modification for T2DM which have been recommended in several diabetes management guidelines (MDES, 2020; MOH *et al.*, 2020; WHO, 2020). However, other factors such as dysregulation of circadian rhythms may also contribute to disease development (Onaolapo and Onaolapo, 2018). The growth of chronobiology and evidence on disturbed circadian rhythm contributed to dysfunction of carbohydrate and macronutrients metabolism and it related to hormone melatonin (Onaolapo and Onaolapo, 2018). From a chronobiological point, glucose metabolism in humans follow a circadian rhythm through diurnal variation of glucose tolerance that typically peaks during day-light hours, when food consumption usually happens and reduces when it comes to night-dark hours when fasting usually occurs (Henry, Kaur and Quek, 2020). Unusual meal timings can cause glucose intolerance by affecting the phase relationship between the central circadian pacemaker and peripheral oscillators in cells of the liver and pancreas in rodents (Bandin *et al.* 2015). Similarly in humans, timed meal intake is also driven by the suprachiasmatic nucleus, play a role in synchronization of circadian rhythms in peripheral tissues, thereby affecting glucose metabolism (Henry, Kaur and Quek, 2020). The effects of diet on circadian rhythmicity clearly involves a relationship between factors such as meal timings and nutrients (chrononutrition), that can contribute to circadian perturbation and influence the manifestation of metabolic disorders such as type 2 diabetes; by extension, circadian timing may also be important in prevention of T2DM development from prediabetes. A new concept is born: perhaps it is not what you eat but when you choose to eat it.

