Energy and macronutrients analysis of dietary record will be performed using Nutritionist ProTM (Axxya Systems, Stafford, TX, USA), based principally on the Nutrient Composition of Malaysian Food and the food product labels. Energy intake will be compared with estimated basal metabolic rate (BMR) to exclude participants who are under-reporting or overreporting their energy intake in their 3-day food diary. BMR is calculated using standard equations based on sex and age provided by FAO/WHO/UNU (1985) (FAO/WHO/UNU 1985). For participants in a non-dieting population, Torun et al. (1996) proposed that a ratio between energy intake and BMR of less than 1.39 and more than 2.24 be considered as under-reporting and over-reporting respectively. These cut-off points will be applied in the present trial. From the 3-day food diary data, The investigator will investigate the dietary intake as reported on the second day of recording. The second day will be selected over the first one to ensure that participants have also include night-time eating in the records. Compare to the later days, which may have been burdened by increasing exhaustion related to the record-keeping, the second day better represents the habitual dietary intake (Ahola et al. 2019). To investigate the energy and macronutrient intakes over the course of the day, five periods will be performed as follows: night (from 00:00 to 04:49), morning (from 05:00 to 09:59), midday (from 10:00 to 13:59), afternoon (from 14:00 to 16:59) and evening (from 17:00 to 23:59), adapted from Ahola et al. (2019). As these periods differed in their duration, energy intake per hour will also be calculated for each of the five periods. In addition, energy and macronutrient intakes per hour (e.g. intakes reported between 10:00 and 10:59 contributed towards the hour "10:00"). Diet quality will be derived from a 177 food items FFQ at second visit, where the Healthy Eating Index (HEI) will be calculated. This FFQ is adapted from the FFQ used by the Malaysian Adults Nutrition Survey (MANS) 2014 (IPH 2014) (Appendix C). Participants will be required to indicate frequency of foods consumed in the last 1 month. Individual portion size will be asked for each food, and pictures of the various portion size will be

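### The night-meal model does not commit to adjusting for total energy intake, so a night-calorie or night-snacking association may reflect eating more overall

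*Combined protocol and SAP*

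**What the plan says.** Section 3, Statistical Analysis, plans a multivariable generalized linear model of night meal pattern on HbA1c, fasting glucose, 2-hour glucose and the CGM profile. The exposure is "last night mealtime either dinner or supper with calories intake, frequency of night snacking, and the total number of the night snacking". The adjustment set is given as: "The potential confounders include sociodemographic characteristics, physical activity, sleep pattern, sedentary behavior, diet quality, and light exposure will be controlled". Neither total energy intake nor BMI is named. The covariate list for the ANCOVA that follows omits both as well.

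Diet quality has two meanings in the protocol:

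- Under Exposure measures it is an HEI score from a food frequency questionnaire. The HEI tables score seven food groups by servings, plus percentage of energy from fat and sodium. There is no total-energy component.
- Later in Statistical Analysis, in the model for lifestyle factors, it is described in brackets as how total energy, carbohydrate, protein and fat are distributed.

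Energy intake is available: "Energy and macronutrients analysis of dietary record will be performed using" nutrient software, and each participant's intake is compared with basal metabolic rate to screen for misreporting. The same section takes dietary intake from the second diary day. Anthropometry is measured at all three visits, but in the analysis BMI appears only as an exposure in a separate logistic regression.

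**The concern.** The Introduction frames the question as timing rather than amount: "perhaps it is not what you eat but when you choose to eat it". The literature review also lists excess calories among the main risk factors for type 2 diabetes, so amount eaten is a rival explanation on the protocol's own account. Someone who eats more over the day will tend to eat more, and snack more often, at night. If the fitted model holds diet quality constant only as an HEI score, a positive night-calorie or snacking coefficient could arise with no effect of night eating. The findings are meant to inform clinical guidelines, so the two explanations need to be told apart.

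**Working it through.** **1. The plan's own figure.** The sizing uses "Linear Multiple Regression Fixed Model, single regression coefficient", with "Effect Size (β -coefficient): 0.13", and "the power was set to 0.9 with 2 sided significance level and alpha error given 0.05". I used noncentral t power with noncentrality √(f²·N) and N − p − 1 degrees of freedom. Entering 0.13 as f² gives N = 83 for 1 to 8 predictors and 84 for 9 or more (up to 20 tried). This agrees with "Total Sample Size: 83 prediabetes individuals", and 83/(1 − 0.5) = 166 to recruit. No stated figure is in dispute here. N = 83 is the planned evaluable number, so it is the relevant one below.

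**2. False positives if total energy is left out.** The documents give neither input, so both are assumptions: r, the correlation of night calories with total energy, and g, the standardised effect of total energy on the glycaemic outcome. The true night-calorie effect is set to zero.

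- Apparent standardised coefficient: b = r × g
- f² = b²/(1 − b²)
- Rejection probability: two-sided 5% test, noncentral t with 7 predictors

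Example: r = 0.5 and g = 0.3 give b = 0.15, f² = 0.0225/0.9775 = 0.0230, noncentrality √(0.0230 × 83) = 1.38, and rejection in 28% of studies.

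| r | g | b | N = 83 | N = 166 |
|---|---|---|---|---|
| 0.3 | 0.1 | 0.03 | 6% | 7% |
| 0.3 | 0.2 | 0.06 | 8% | 12% |
| 0.3 | 0.3 | 0.09 | 13% | 21% |
| 0.5 | 0.1 | 0.05 | 7% | 10% |
| 0.5 | 0.2 | 0.10 | 15% | 25% |
| 0.5 | 0.3 | 0.15 | 28% | 49% |
| 0.7 | 0.1 | 0.07 | 10% | 15% |
| 0.7 | 0.2 | 0.14 | 25% | 44% |
| 0.7 | 0.3 | 0.21 | 49% | 79% |

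Simulation at N = 83 (4,000 replicates, six unrelated covariates) gave the following without and with total energy in the model: 13.5% and 4.9% (r = 0.5, g = 0.2); 26.6% and 5.6% (r = 0.5, g = 0.3); 47% and 5.2% (r = 0.7, g = 0.3).

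**3. What measurement error leaves behind.** If recorded energy has reliability λ, the coefficient remaining after adjustment is b = r·g·(1 − λ)/(1 − r²·λ). With r = 0.5, g = 0.3 and an assumed λ = 0.5, b = 0.15 × 0.5/0.875 = 0.086. The false-positive rate at N = 83 is then about 11% to 12%, against about 27% unadjusted. At λ = 0.3 it is about 17%. One diary day will have lower reliability than an average of several.

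**4. Cost in precision.** With f² held at 0.13, two more covariates leave N at 83 or 84. If 0.13 is instead the effect before adjustment, f² shrinks to 0.13 × (1 − R²), where R is the assumed multiple correlation of the exposure with the added covariates. With 9 predictors:

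| R | f² | Power at N = 83 | N for 90% | Recruit at 50% dropout |
|---|---|---|---|---|
| 0.3 | 0.1183 | 87% | 91 | 182 |
| 0.5 | 0.0975 | 80% | 110 | 220 |
| 0.7 | 0.0663 | 64% | 161 | 322 |

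**The case against.** A reader might infer that the plan flatly fails to adjust for energy, so that eating more cannot be separated from eating later. The documents do not support that.

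- **Diet quality may include energy.** It is a named covariate, and one of its two descriptions mentions total energy. The confounder list is also worded as open. This stands against a claim of outright omission. It does not amount to a commitment to adjust, because the other definition excludes total energy.
- **The data allow separation.** Mealtime and night calories are both listed in the exposure and could enter one model, energy by period of day is planned, and clock-time cut-offs at 2000, 2100 and 2200 are examined. The gap is in the stated model. Entering mealtime alongside night calories does not, however, protect the night-calorie coefficient from total energy.
- **The figures concern night calories only.** Nothing in the documents shows how far the clock time of the last meal correlates with total energy, so no rate can be given for that coefficient.
- **The HEI is not independent of amount eaten.** Food groups are scored by servings and sodium in absolute milligrams. It is a partial proxy, and along with the other planned covariates and the misreporting exclusion it could reduce the bias below the tabled values.
- **Total energy may lie on the pathway.** Night snacking can itself raise daily energy, and adjustment then changes the question to one at equal intake. This is correct, and is the reason to show both models.
- **BMI may be a mediator.** This stands. It limits BMI to a sensitivity analysis.

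**Conclusion.** The concern holds as a gap in specification. The night-meal model puts night calories and snacking in the exposure, does not name total energy as a covariate, and relies on a diet-quality term with two incompatible definitions. If the HEI definition is used, the false-positive rate for the night-calorie term at N = 83 is about 6% to 49% over the assumed range, against a nominal 5%. At the low end the harm is negligible. At the middle values (r = 0.5, g = 0.2) it is about 15%. The range rests entirely on assumed correlations and effects, with no true night effect and no help from the other covariates. The correction is worth making because it is cheap and bears directly on the study's own question.

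**What to change.** In Statistical Analysis:

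1. Give diet quality one definition, the HEI score, and use it wherever the term appears.
2. Add total daily energy from the 3-day diary as a separate covariate in the night-meal models. Express night intake as a share of daily energy, and state that the coefficient is then a timing effect at equal total energy.
3. Report the model without total energy alongside, because night eating may itself raise total energy.
4. For this covariate, average energy over all valid diary days instead of using the second day alone, and acknowledge that some residual confounding will remain.
5. Report a version with baseline BMI added as a sensitivity analysis only, noting that attenuation may reflect mediation.
6. State whether mealtime and night intake enter the same model.

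The cost is analysis wording and 1 to 2 degrees of freedom, with no new data. Precision falls if night and total energy are strongly collinear, to 64% power at N = 83 in the worst case shown.
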